### **Patients allocation**

Patients were allocated into one of three groups of treatment by Heart Team. Patients consecutively admitted in the Department of Cardiac Surgery #1 and #2. All patients who admitted in the Department of Cardiac Surgery #1 allocated into off-pump CABG group. Patients who admitted in the Department of Cardiac Surgery #2 allocated into off-pump CABG group, on-pump CABG group (when have proximal lesions of RCA or LCx), off-pump CABG group (when have more distal lesion of coronary arteries) or pump-assisted CABG group (when have difusse coronary artery lesions). Heart Team includes three or more cardiac surgeons who performs off-pump, on-pump or pump-assisted CABG more than 10 years, two or more interventional cardiologists, one neurologist, two or more anesthesiologist, two or more reanimatologist, one perfusologist and two cardiologist. After debating patients were alocated into one of threy groups for elective CABG.

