Title	Assessment of Myocardial Ischemic-Reperfusion Injury During Off- and On- Pump CABG (AMIRI-CABG) ClinicalTrials.gov Identifier: NCT03050489	
Authors *	[name]	
Trial design	Prospective non-randomized single center	
Methods		
Participants	Eligibility criteria: multivessel coronary artery disease with indications for elective coronary artery bypass grafting	
Interventions	Group 1: off-pump CABG Group 2: on-pump CABG Group 3: pump-assisted CABG (on-pump CABG without aortic cross-clamping)	
Objective	To compare level of MPO between three groups of intervention	
Primary objective	To compare ischemic-reperfusion injury between three groups of intervention	

Assessment of Myocardial Ischemic-Reperfusion Injury During Off- and On- Pump CABG  
 (ClinicalTrials.gov Identifier: NCT03050489). Corresponding author: [name]  
[[contact]](mailto:[contact]) [contact]

Date of the document 06 December 2016

Secondary objective	To assess ability of MPO to predict worse outcome (death) To assess relation between MPO and TnI	
Outcome	MPO level after CABG, death after CABG	
Randomization	Non-randomized allocation. Heart Team decision.	
Blinding (masking)	None	
Results		
Numbers randomized	Number of participants screened n=500  Allocated (non-randomized): off-pump CABG (n=181), on-pump CABG (n=128), pump-assisted CABG (n=27)	
Recruitment	Complete	
Numbers analyzed	Off-pump CABG: 181 On-pump CABG: 128 Pump-assisted CABG: 27	
Outcome	Could MPO predict death during 30 days after CABG	
Harms	Important adverse events or side effects	
Conclusions	CPB activates leucocytes that cause myocardial damage  Preoperative MPO level could evaluated as a predictor of myocardial damage and worse outcome after CABG	
Trial registration	ClinicalTrials.gov Identifier: NCT03050489	
Funding	Assessment of regenerative ability after cardiac surgery	

*Table 2 Statistical analysis synopsis*

Assessment of Myocardial Ischemic-Reperfusion Injury During Off- and On- Pump CABG ClinicalTrials.gov Identifier: NCT03050489	
Hypothesis	Ischemic – reperfusion injury are comparable between groups
Primary objective	To compare ischemic-reperfusion injury during off-pump, on-pump and pump – assisted CABG
Secondary objective	To assess ability of myeloperoxidase to predict worse outcome after CABG

Assessment of Myocardial Ischemic-Reperfusion Injury During Off- and On- Pump CABG  
 (ClinicalTrials.gov Identifier: NCT03050489). Corresponding author: [name]  

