## Study Design

Prospective single center non-randomized clinical trial.

**Study Centers:** First Saint Petersburg State Medical University.

**Number of groups:** 3

Intervention:

Group 1: off-pump CABG

Group 2: on-pump CABG

Group 3: pump-assisted CABG (on-pump CABG without aortic cross-clamping)

**Sample size:** >300.

*Table 3 Number of patients*

Intervention	Number of patients	
	Planned	Actual
off-pump CABG	100	181 (175)
on-pump CABG	100	128 (127)
pump-assisted CABG	100	27 (33)
Total	300	336
Conversion	N/A	6

181 patient planned for elective CABG. There were 6 conversions to pump – assisted CABG (on-pump CABG without aortic cross-clamping). 175 received off-pump-CABG. 27 patient planned for elective pump – assisted CABG (on-pump CABG without aortic cross-clamping). 33 pump – assisted CABG were performed.

**Primary Endpoint:** MPO level after operation.

**Secondary Endpoints:** low output syndrome, length of stay in intensive care unit, length of stay in hospital, inotrope and vasopressor agents demand, duration of pulmonary ventilation, end systolic volume, end diastolic volume, ejection fraction, reoperation, renal dysfunction, atrial fibrillation, death during 30 days after CABG, stroke during 30-days after CABG.

Assessment of Myocardial Ischemic-Reperfusion Injury During Off- and On- Pump CABG (ClinicalTrials.gov Identifier: NCT03050489). Corresponding author: [name] [[contact]](mailto:[contact]) [contact]

Date of the document 06 December 2016

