### Primary endpoint analysis

Hypothesis: MPO levels after procedure are different between groups.

Hypothesis testing:

- Normality test (Kolmogorov-Smirnov test, Shapiro-Wilk test)

Group comparing:

Continuous variables

- Non-normal distribution: Kruskal-Wallis test with adjustment for multiple comparisons

*Table 6 Myeloperoxidase variables specifications*

Characteristic	Variable name in database	Test
MPO level before procedure	MPOPreOp	Kruskal-Wallis test
MPO level after procedure	MPOPostOp	Kruskal-Wallis test

*Table 7 Myeloperoxidase before and during coronary artery bypass grafting (CABG)*

Variables	off-pump CABG (N=181)	on-pump CABG (N=128)	pump-assisted CABG (N=27)	P Value*
MPO before CABG				0.2904
Nmiss (%)	34 (18.8)	21 (16.4)	9 (33.3)	
Mean±SD	35.8±32.1	39.9±30.6	29.2±14.8	
Min–Max	2.8–237.8	4.0–168.9	5.6–65.4	
Median (IQR)	27.7 (17.0–41.0)	31.0 (19.0–48.7)	29.0 (18.7–34.0)	
MPO after CABG				<.0001
Nmiss (%)	28 (15.5)	26 (20.3)	13 (48.1)	

Date of the document 06 December 2016

Variables	off-pump CABG (N=181)	on-pump CABG (N=128)	pump-assisted CABG (N=27)	P Value*
Mean±SD	96.2±75.3	210.9±138.7	175.0±102.6	
Min–Max	9.1–410.3	16.7–824.6	63.4–374.5	
Median (IQR)	66.5 (41.3–135.8)	184.3 (135.0–250.0)	144.7 (95.0–284.9)	

\* Kruskal-Wallis test, Nmiss – number of missing values, SD – standard deviation, IQR – interquartile range, CABG – coronary artery bypass grafting

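### Admitting department and lesion site decided the technique, yet neither enters any table or model, so off-pump versus on-pump is partly a comparison of departments and of anatomy

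*Combined protocol and SAP*

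**What the plan says.** Table 1 describes allocation as "Non-randomized allocation. Heart Team decision". The Patients allocation section is more specific. For the first department it gives a fixed rule: "All patients who admitted in the Department of Cardiac Surgery #1 allocated into off-pump CABG group". For the second, technique depended on the coronary lesions: "on-pump CABG group (when have proximal lesions of RCA or LCx), off-pump CABG group (when have more distal lesion of coronary arteries"). Patients there with diffuse disease were placed in the pump-assisted group. The section ends by saying that the Heart Team debated cases and placed patients in one of the three groups.

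Table 1 gives the allocated numbers: "off-pump CABG (n=181), on-pump CABG (n=128), pump-assisted CABG (n=27"). Study Design adds: "There were 6 conversions to pump – assisted CABG (on-pump CABG without aortic cross-clamping"). The department of those six patients is not given, and neither is the number of patients per department.

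The primary endpoint section sets out "Hypothesis: MPO levels after procedure are different between groups" and tests it with an unstratified Kruskal-Wallis test. The conclusions row of Table 1 then states a cause: bypass activates white cells, and these injure the heart muscle.

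**The concern.** Two variables determined which operation a patient was allocated to: the admitting department and, within Department #2, the site of the lesions. Neither is in the baseline tables (Tables 4 and 5), the MPO comparison (Table 7), the MPO and troponin ANCOVAs (Tables 8 to 21), the death model (Tables 22 and 23), the missingness model (Tables 26 and 27) or the outcome tables (Tables 29 to 31).

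The off-pump column pools two departments, while both bypass columns come, by allocation, from one. If care, sampling or case mix differed between departments, that difference enters every off-pump versus on-pump contrast, including the primary endpoint. The same holds for anatomy, because within Department #2 proximal lesions went on-pump and more distal lesions off-pump. A reader cannot judge the size of either effect, because not even the counts by department are printed. The causal statement in Table 1 needs the contrast to reflect technique.

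**Working it through.** **1. Could a department term be in a fitted model?** Count the degrees of freedom of the listed terms against the printed model df.
- Post-suture MPO (Tables 9 and 10): 1 + 2 + 2 + 1 + 1 + 1 + 1 = 9; printed 9.
- Troponin day 1, all groups (Tables 12 and 13): 1 + 1 + 1 + 1 + 1 + 2 + 1 + 1 + 1 + 2 + 2 = 14; printed 14.
- Troponin, on-pump (Tables 15 and 16): eight single-df terms; printed 8.
- Troponin, off-pump (Tables 18 and 19): three terms; printed 3.

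No df is left for department or lesion category in any of these. The off-pump troponin model omits department although that group spans both departments.

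**2. How much of the MPO gap could department explain?** Inputs from Table 7: off-pump 96.2±75.3 (153 measured), on-pump 210.9±138.7 (102 measured). The gap is 210.9 − 96.2 = 114.7 ng/ml. Its standard error is √(75.3²/153 + 138.7²/102) = 15.0, so the approximate 95% interval is 85.3 to 144.1.

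Let f be the Department #1 share of the measured off-pump patients (an assumption, since it is not reported). For department to explain the whole gap, Department #2 off-pump patients must average 210.9. The two off-pump means then differ by 114.7/f, and the Department #1 mean is 210.9 − 114.7/f.
- f = 0.50: difference 229.4, Department #1 mean −18.5, which is impossible.
- f = 0.75: difference 152.9, Department #1 mean 58.0.

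The printed SD gives a tighter limit. The variance between departments alone is f(1 − f)(114.7/f)² = [(1 − f)/f] × 114.7², and it cannot exceed 75.3². Hence (1 − f)/f ≤ (75.3/114.7)² = 0.431, so f ≥ 1/1.431 = 0.70.

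If Department #2 off-pump patients must also have the on-pump SD, the condition is (1 − f) × 138.7² + [(1 − f)/f] × 114.7² ≤ 75.3² = 5670, with no spread at all allowed in Department #1. At f = 0.84 the left side is 3078 + 2506 = 5584, which fits. At f = 0.835 it is 3174 + 2600 = 5774, which does not. The limit is about 0.84.

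To explain half the gap (57.35), the off-pump departments must differ by 57.35/f: 114.7 ng/ml at f = 0.50 (means 153.6 and 38.9), or 76.5 at f = 0.75.

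**3. Binary outcomes (Table 29).** Take the largest Department #2 off-pump number n for which n × the on-pump rate does not exceed the observed off-pump events. Then f = (181 − n)/181. This assumes **no events at all in Department #1**.
- Atrial fibrillation: 26/(27/128) gives n = 123; 58/181 = 32%.
- Kidney damage, raised creatinine plus hemodialysis (49 + 2 = 51 versus 70 + 6 = 76): 51/(76/128) gives n = 85; 96/181 = 53%.
- Bleeding: 3/(14/128) gives n = 27; 154/181 = 85%.
- Multiorgan dysfunction: 2/(12/128) gives n = 21; 160/181 = 88%.

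These are extreme bounds. The kidney figure, for example, needs 0 of 96 in Department #1 against about 59% in Department #2.

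**The case against.** The strongest reply is that the study is openly non-randomized, exploratory and single-centre, that one Heart Team is described, that the department rule is disclosed, and that no figure shows outcomes differing by department. Table 5 also shows similar groups (p from 0.1141 to 0.9090), including Syntax Score I. All of this is true, and it limits the severity. It does not remove the point: Table 5 contains neither of the two variables that set allocation, and department practice would act after baseline.

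Several stronger readings are tempting but not supported.
- A reader might match quartiles (off-pump upper 135.8, on-pump lower 135.0) and infer that department could account for all of the MPO difference at a Department #1 share of two-thirds. At f = 2/3 the between-department SD alone would be √0.5 × 114.7 = 81, above the printed 75.3. The same device fails for day-1 troponin (quartiles 1.0 and 1.8), because it counts off-pump values above 1.0 as if they were above 1.8.
- A reader might infer that every patient put on bypass came from Department #2. That holds for allocation only, because the department of the six converted patients is not stated. As those conversions were to pump-assisted surgery, off-pump versus on-pump as allocated is not affected.
- A reader might infer that department is missing from the database. The specification tables list variables for particular tests, so they show only that it is not used.
- A reader might take ICU stay, ventilation and inotrope use to be products of departmental routine. No section describes separate routines, and the secondary tables print p-values without causal claims.

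**Conclusion.** The point holds as a should-fix. By allocation, off-pump versus on-pump is partly a comparison of departments and of coronary anatomy, and nothing in the plan examines either. No actual department effect is shown, and its possible size depends on the unreported share f.

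For the primary endpoint, department alone could account for the full 114.7 ng/ml only if at least about 70% of measured off-pump patients came from Department #1, or about 84% if the SD must match as well. Inflation of the MPO gap is therefore more plausible than creation of it. The 32%, 53%, 85% and 88% thresholds for the binary outcomes are outer limits that rest on zero Department #1 events, and they should not be read as likely sizes. All these bounds treat the on-pump arm as wholly Department #2, as the allocation text implies.

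**What to change.** Add admitting department and the lesion category used for allocation (proximal RCA or LCx, more distal, diffuse) to the dataset and to Table 5. For off-pump patients, report counts, baseline data and outcomes by department (MPOPostOp, troponin day 1 and the Table 29 outcomes). Note that lesion mix may differ between departments, so this is not a clean estimate of a department effect.

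Keep the planned comparison and add two sensitivity analyses:
- (a) off-pump versus on-pump within Department #2, adjusted for lesion category where the groups overlap;
- (b) Department #1 off-pump patients with proximal RCA or LCx lesions versus Department #2 on-pump patients. This matches lesion type but varies department and technique together.

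Neither should replace the main comparison. In (a), lesion site takes the place of department as the confounder. A department covariate alone would be estimated from off-pump patients only and would assume no department-by-technique interaction.

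Limit the causal wording in Table 1 to differences that hold in both (a) and (b). State the department of the six converted patients. Reconcile the Heart Team description in Table 1 with the Department #1 rule.

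The cost is some extraction from admission records and existing angiograms or Heart Team notes, with no new patients. The drawbacks are smaller, less precise comparisons and residual anatomical confounding within Department #2.

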### **Study objectives**

- To compare ischemic-reperfusion injury after off-pump, on-pump and pump-assisted - CABG

### **Primary objective**

- To compare MPO level before and just after performing coronary anastomosis during off-pump CABG, on-pump CABG and pump-assisted CABG (with cardiopulmonary bypass without aortic cross-clamping)
- To compare TnI level between groups

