[[contact]](mailto:[contact]) [contact]

Date of the document 06 December 2016

Type of trial	Prospective non-randomised single-centre
Type of research	Exploratory
Timeline	2015-2019
Groups	Off-pump  On – pump  Pump-assisted (on-pump without aortic cross-clamping)
Sample size estimation	> 300 patients
Planned sample size	Average: 300  Off-pump: 100  On-pump: 100  Pump-assisted: 100
Actual sample size	Average: 336  Off-pump: 181 (conversion 6)  On-pump: 128  Pump-assisted: 27
Baseline characteristics comparing	Testing for type of distribution of baseline characteristics:  ANOVA for normal distribution  Kruskal-Wallis test with multiple groups comparison adjustment for non-normal distribution  Chi-squared test or exact Fisher's test for nominal data
Statistics hypothesis testing	ANOVA/ANCOVA for MPO level, troponin I level
Missing Data Handling	Drop observations with missing data
Evaluating of reason of missingness	Hypothesis: Missing data depend on severity of complications  Hypothesis testing with logistic regression model: Missingness = complications

Assessment of Myocardial Ischemic-Reperfusion Injury During Off- and On- Pump CABG  
(ClinicalTrials.gov Identifier: NCT03050489). Corresponding author: [name]  
[[contact]](mailto:[contact]) [contact]

Date of the document 06 December 2016

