#### Ischemic – reperfusion injury analysis (TnI level 1st day after CABG)

Hypothesis: TnI level 1st after CABG depends on length of operation, length of cardiopulmonary bypass, MPO level before procedure and just after suture performing

Method of hypothesis testing: ANCOVA

ANCOVA model:  $LGTnI1 = LGMPOPostOp LGMPOPreOp CPBTYPE LGMPOPreOp*CPBTYPE AoClamp CPBTime AoClamp*CPBTime OpTime CPBTime* OpTime AoClamp*OpTime$

*Table 11 Variables descriptions*

Variable	Description	Note
TnI1	Troponin I level 1 st day after procedure	Continuous variable
LGMPOPostOp	Logarithm of MPO level during CABG (after suture performing)	Log – transformation for normal distribution
LGMPOPreOp	Logarithm of MPO level before CABG (after suture performing)	Log – transformation for normal distribution
CPBTYPE	Group of intervention	1 – off-pump CABG 2 – on – pump CABG 3 – pump-assisted CABG
AoClamp	Length of aortic cross-clamping, min	Continuous variable
CPBTime	Length of cardiopulmonary bypass, min	Continuous variable
OpTime	Length of procedure, min	Continuous variable
*	Interaction effect	

*Table 12 Characteristics of model*

Source	Sum of Squares	df	Mean Square	F	p	Eta Square

Assessment of Myocardial Ischemic-Reperfusion Injury During Off- and On- Pump CABG (ClinicalTrials.gov Identifier: NCT03050489). Corresponding author: [name] [[contact]](mailto:[contact]) [contact]

Date of the document 06 December 2016

Model	249.3	14	17.8	10.4	0.0001	0.44
-------	-------	----	------	------	--------	------

*Table 13 General linear model characteristics*  $LGTnI1 = LGMPOPostOp LGMPOPreOp CPBTYPE$   
 $LGMPOPreOp*CPBTYPE AoClamp CPBTime AoClamp*CPBTime OpTime CPBTime* OpTime$   
 $AoClamp*OpTime$

Source	Sum of Squares (Type III)	df	Mean Square	F	p	Partial Eta Squared
LGMPOPostOp	2.0	1	2.6	1.2	0.3	0.006
LGMPOPreOp	0.8	1	0.8	0.5	0.5	0.002
AoClamp	2.3	1	2.3	1.4	0.2	0.007
CPBTime	2.2	1	2.2	1.3	0.3	0.007
OpTime	23.3	1	23.3	13.6	0.0003	0.07
CPBType	3.9	2	1.9	1.1	0.3	0.01
CPBTime*OpTime	0.7	1	0.7	0.4	0.5	0.002
AoClamp*CPBTime	0.4	1	0.4	0.22	0.6	0.001
AoClamp*OpTime	3.5	1	3.5	2.1	0.2	0.01
LGMPOPostOp*CPBTYPE	4.1	2	2.1	1.2	0.3	0.01
LGMPOPreOp*CPBTYPE	0.4	2	0.2	0.1	0.9	0.001

**Summary:** troponin I level 1st day postoperatively depends on length of operation

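### Troponin I is a primary objective with no day or measure fixed, and the plan names two unranked methods for it that give different day-1 verdicts (p<.0001 against p=0.3)

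*Combined protocol and SAP*

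**What the plan says.** - **Objective.** Primary objective has two items: MPO before and just after the anastomoses, and "To compare TnI level between groups". The second gives no day, scale or test.
- **Endpoints.** Study Design gives the primary endpoint as "MPO level after operation". TnI is not in that section's secondary list either.
- **Test in the synopsis.** Table 2, row on statistical hypothesis testing: "ANOVA/ANCOVA for MPO level, troponin I level". No day is given.
- **Test in the body.** The TnI group comparisons for days 1 to 5 are in the first Table 30, under Secondary Endpoint Analysis, where the named test is Kruskal-Wallis.
- **ANCOVA.** Only day-1 TnI is modelled. The hypothesis for the whole-cohort model is that TnI "after CABG depends on length of operation, length of cardiopulmonary bypass, MPO level before procedure and just after suture performing". Surgical group is not part of that hypothesis, although CPBType is in the model.
- **Hypothesis.** Table 2: "Ischemic – reperfusion injury are comparable between groups". Primary endpoint analysis: "Hypothesis: MPO levels after procedure are different between groups".
- **A further measure.** Definitions describes ischemic-reperfusion injury as a yes/no outcome: TnI above the upper reference limit without type 5 infarction. No day is given, and no group comparison of it is reported.

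**The concern.** A primary objective needs one stated comparison that answers it. For TnI a reader can choose among five days, a level or a binary definition, and two methods. The documents already contain results, and the choice of method decides whether day-1 TnI counts as different between techniques.

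Two misreadings are at stake. A reader who follows the synopsis goes to the ANCOVA group row, finds p=0.3, and may conclude that technique does not matter for troponin. That section's own summary names only length of operation. And because the synopsis hypothesis is that injury is comparable, any non-significant row can be taken as support for it, including rows that rest on a small and selected part of the cohort.

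**Working it through.** **1. Reproduce the ANCOVA group row.** Table 12 prints the model line "249.3 14 17.8 10.4 0.0001 0.44" (SS, df, MS, F, p, eta squared). Table 13 prints "CPBType 3.9 2 1.9 1.1 0.3 0.01" (SS, df, MS, F, p, partial eta squared).

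- Error mean square = MS / F = 17.8 / 10.4 = 1.71.
- Error SS = 249.3 / 0.44 − 249.3 = 317.3.
- Error df = 317.3 / 1.71 ≈ 185 (182 to 189 as eta squared runs from 0.445 to 0.435).
- Group F from its SS = (3.9 / 2) / 1.71 = 1.14.
- For 2 numerator df, p = (1 + 2F/d)^(−d/2). With d = 186, F = 1.1 gives 0.335 and F = 1.14 gives 0.322. Both round to the printed 0.3.

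**2. Patients in that row.** n = error df + model df + 1 ≈ 185 + 14 + 1 = 200. The model needs post-anastomosis MPO, which Table 25 shows for only 14 of the 27 pump-assisted patients.

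**3. What the row conditions on.** The stated formula has 12 df: eight single-df covariate and covariate-interaction terms, group (2), and preoperative log MPO by group (2). Table 12 has 14. The extra 2 are the postoperative log MPO by group interaction, printed in Table 13 but absent from the formula. The row therefore compares techniques at equal post-anastomosis MPO, clamp time, bypass time and operation time. Pump-assisted surgery is defined as bypass without cross-clamping, and off-pump surgery uses no bypass, so clamp and bypass time largely define the groups. Post-anastomosis MPO is itself the primary endpoint. No centring is stated. If there was none, the Type III group row compares groups at log MPO of zero, that is 1 ng/ml, below the smallest values in Table 7 (2.8 before, 9.1 after).

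**4. The daily comparisons.** First Table 30; measured = 336 minus the sum of the three missing counts.

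| Day | Missing (off, on, assisted) | Measured | Missing % | Printed p |
|---|---|---|---|---|
| 1 | 17, 10, 1 | 308 | 8.3 | <.0001 |
| 2 | 104, 39, 9 | 184 | 45.2 | <.0001 |
| 3 | 149, 90, 21 | 76 | 77.4 | 0.1936 |
| 4 | 168, 108, 22 | 38 | 88.7 | 0.3843 |
| 5 | 158, 106, 23 | 49 | 85.4 | 0.2222 |

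These p-values cannot be recomputed without patient data. As a rough check, lognormal data simulated from the printed medians and quartiles (2000 runs per day) gave median p far below 0.0001 on days 1 and 2, and non-significant medians on days 3 and 5. Day 4 came out near 0.03, with 58% of runs below 0.05, which is too crude to dispute the printed value.

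**5. Are the later days informative?** Patients measured late differ from those measured on day 1. From Table 31, off-pump patients with low output syndrome make up (15 − 3) / 164 = 7% of those measured on day 1 and (15 − 10) / 13 = 38% on day 4. On-pump, the shares are (15 − 2) / 118 = 11% and (15 − 9) / 20 = 30%. In the same simulation, a difference of day-2 size reached p<0.05 in 90%, 53% and 71% of runs at the day 3, 4 and 5 group sizes.

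**The case against.** The best defence has four parts.

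- **The trial does have a named primary comparison.** This stands. Study Design gives MPO after operation, and Primary endpoint analysis tests it by Kruskal-Wallis. A reader might infer that nothing decides the trial; the documents do not support that. The gap is confined to the TnI objective, apart from the synopsis also naming ANOVA/ANCOVA for MPO.
- **The TnI results do not conflict.** This also stands. It is tempting to say that the plan answers its primary question both ways. It does not: the ANCOVA row is a conditional contrast in a smaller sample, and days 3 to 5 are sparse and selected. Neither contradicts the unadjusted day-1 result. But this is the reason to say which analysis answers the objective, because the synopsis points to the one that does not.
- **The study is exploratory, and the positive results are robust.** A reader might infer that unadjusted multiplicity undermines them. At an assumed 0.05 per test (the plan states no alpha), five independent daily tests give 1 − 0.95^5 = 0.23. That figure does not measure this problem, and days 1 and 2 survive Bonferroni over six tests (6 × 0.0001 = 0.0006). The exploratory label still does not say which result answers a primary objective.
- **The two hypotheses may be compatible.** One concerns injury and the other MPO, or they may be a null and an alternative. No summary claims comparability from a non-significant group row. That is fair, so the harm is a risk of misreading and not a demonstrated misreport.

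One could add that day 1 is implied because only day 1 is modelled. That is an inference, and it leads to the ANCOVA.

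**Conclusion.** The point holds as a specification fault with a visible consequence. The TnI primary objective has no designated day or measure, TnI is in neither endpoint list, and two methods are named without ranking. For day 1 the choice moves the verdict from p<.0001 to p=0.3 (0.32 to 0.34 recomputed). The test named in the synopsis, as modelled, does not estimate the between-group comparison that the objective asks for. It adjusts for consequences of technique and uses about 200 patients where 308 have a day-1 value. Non-significance in that row, or on days 3 to 5, is not evidence of comparability.

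This rests on three assumptions: the Table 30 p-values, which carry no footnote, come from the Kruskal-Wallis test named for their section; the error df follows from the rounded figures in Table 12; and the remark about 1 ng/ml applies only if covariates were not centred. No reported positive result is overturned. The unadjusted comparison in this non-randomised study remains open to confounding by allocation.

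**What to change.** - Keep MPOPostOp by Kruskal-Wallis as the primary endpoint.
- In Table 2, Study Design, Primary objective and Secondary Endpoint Analysis, state that the TnI objective is answered by the unadjusted between-group comparison of the day-1 TnI level, Kruskal-Wallis, 308 of 336 measured.
- In Table 2, replace ANOVA/ANCOVA as the group-comparison test for MPO and TnI. Label the CPBType rows of the MPO and whole-cohort TnI ANCOVAs (Tables 10 and 13) exploratory, and say that they do not estimate the total effect of technique.
- In Table 2, change the hypothesis from comparable to different, and add that non-significance is not evidence of comparability.
- Keep days 2 to 5 with their p-values and patient counts, labelled exploratory and subject to heavy missingness. Deleting the non-significant ones would make reporting more selective.
- Disclose that the day and test were designated after the results were seen, and claim no family-wise error control. A gate already known to be passed would control nothing.

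The cost is wording only, with no new data or analysis. The later days and the ANCOVA group rows can no longer support a primary claim, and the day-1 result has to be reported as post hoc.
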